10. POTENTIAL BENEFITS TO SUBJECTS

Subjects might not benefit from being in this research study. The potential benefits include learning more about themselves through clinical assessments, decreased risk of suicidal ideation recurrence, and possible reduction of depressive symptoms.

11. COSTS FOR PARTICIPATION

There are no costs that subjects may be responsible for because of participation in this research.

12. PAYMENT FOR PARTICIPATION

Subjects will receive \$40 for the baseline assessment, \$30 for each clinical assessment (day 14, day 30, and day 60 from the first RS-tDCS session), and \$30 for their time when sending the device back in a pre-paid package by mail, receiving a maximum compensation of \$160 through Amazon gift card. Subjects will receive either a text message or email with an Amazon gift code, or a mailed Amazon gift card, following the completion of each clinical assessment.

13. SUBJECT WITHDRAWALS

Subjects may be removed from the study without their consent if they appear to be harmed by participating. Subjects will also be removed from the study if they do not tolerate the tDCS stimulation during the tolerability test (please, see "Study procedures"). Subjects will also be removed from the study if they initiate treatment with electroconvulsive therapy or transcranial magnetic stimulation at any moment during the trial. Finally, women subjects will be removed from the study if they become pregnant or planning to become pregnant during the time of the study comprehending the RS-tDCS sessions No new information identifying the subject will be gathered after the withdrawal date. Information that has already been gathered may still be used for research purposes.

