7. The level of side effects will be assessed at the end of each session on a 0 (not at all) to 10 (highest degree) scale used by Ahn et al. (2019) (37), which includes the following symptoms: 1. Itching; 2. Burning; 3. Headache; 4. Fatigue; 5. Nervousness; 6. Dizziness; 7. Difficulty concentrating. The total score is the sum of the 7 items, varying from 0 to 70. Higher scores indicate higher levels of side effects.

8. Treatment emergent event review: after each RS-tDCS session and clinical assessment, subjects will be asked "Have you had any new symptoms, new medical conditions or been started on new medication/treatment since we last saw you?". This information will help research staff to judge about potential adverse events related to the trial. In addition, changes in treatment will help researchers to account for them in data analysis and the study's results interpretation.

4.1. **STUDY INTERVENTION**

The study intervention is tDCS treatments delivered by the Soterix Medical mini-CT device (https://soterixmedical.com/research/remote/mini-CT). The device is a nonsignificant risk (NSR) device study because it does not meet the definition of a significant risk device under §812.3 (m) of the investigational device exemptions (IDE) regulation (21 CFR §812)

(https://www.accessdata.fda.gov/scripts/cdrh/cfdocs/cfcfr/CFRSearch.cfm?fr=812.3).

The Soterix Medical mini-CT device for the RS-tDCS includes: (1) 1 x 1 mini-CT tDCS device; (2) SNAPstrap headgear, a "cap"-like placement for simple positioning and uniform electrode placement; (3) SNAPpads (individually-packaged pre-moistened sponge), and snap connectors (Figure 1) (39).

[figure not shown]

Figure 1. Remotely supervised (RS-tDCS) Equipment. (1) 1 x 1 mini-CT tDCS device; (2) SNAPstrap headgear: "cap"-like placement for simple positioning and uniform electrode placement; (2a) markers for guidance in placement; (2b) electrode polarity labeling with fixed wiring. (3) SNAPpad: (3a) individually-packaged pre-moistened sponge; perforated packaging for easy opening; (3b) snap connectors. (adapted from Pilloni, G., A. et al., Brain Stimul 15(3): 707-716, http://creativecommons.org/licenses/by-nc-nd/4.0/, DOI: 10.1016/j.brs.2022.04.014). The figure at the bottom simulates an RS-tDCS session.

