7. CONSENT PROCESS

Informed consent will be obtained using the institutional review board (IRB)-approved form inperson, in a private setting, and through a paper copy.

Inform consent process includes a detailed description of the study procedures, and statements regarding subjects' rights to withdraw from the procedure at any time without consequences. It is explained to subjects in easy-to-understand language. Consent is documented by the subject's signature on the consent form, accompanied by the signature of a research team member. During consent and throughout the study, it is emphasized that participation or non-participation in the study does not affect the patient's treatment at the hospital. Likewise, they are advised to withdraw their participation in the study at any time. The limits of confidentiality are also explained, including the potential to break confidentiality in the event of acute risk of suicidal behavior or violence or disclosures of unreported physical or sexual abuse of a child.

Consent includes an authorization for staff to access subjects' electronic hospital medical records. Research staff collects information from records related to admission and discharge dates, suicidal ideation, method and circumstance of self-harming behavior, diagnoses, and medication.

Subjects who consent to research participation are given a full research assessment battery. Those who do not consent to participate in the research study return to receiving routine

care provided by the referring clinical service.

To minimize the possibility of coercion or undue influence, the consent process is carried out by research staff employed for the study and will not involve any members of the patient's treatment scheme. Patients are encouraged to ask questions about participation in the study. They may take as much time as necessary to consider participation and consult with family members or the treatment team. Patients are reminded that participation is voluntary, and they may withdraw from the study anytime.

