device, how to turn it on/off, and insert the unlock codes for one-time use; 2) to assess if the subject tolerates the protocol electric current through the tolerability test; 3) answer any questions the subjects may have. As the Soterix Medical mini-CT device will be with the subjects during the RS-tDCS sessions, subjects will be asked to sign an IRB-approved device loan agreement at the baseline.

Clinical questionnaires will be re-administered at day 14 [+ 7 days], day 30 [+ 7 days], and day 60 [+ 10 days] from the first RS-tDCS session session15 (Figure 3). While we aim to reach subjects on the phone for follow-up, research staff may email or text subjects to schedule the RS-tDCS sessions and clinical assessments. Subject identifying information and protected health information (PHI) is not exchanged in the text messages themselves. Detailed information about text messaging is included under the "Privacy and Confidentiality of Subjects and Research Data" section. Security risks associated with text messaging are described in detail during consent.

After baseline assessment, research staff not involved in the RS-tDCS supervisions and clinical assessments will randomize the subject to active or sham control group and set up the device condition (active or sham), program the intensity for the active condition (either 2.0 mA or 1.5 mA, according to the tolerability test) and duration (30 minutes) of each session, and get the device unlock codes for one-time use to be provided by the research staff to the subject immediately before each session. The discharge day will be tracked daily by the research staff through the electronic hospital medical record. Once the subject is discharged, research staff will deliver the RS-tDCS device by mail to the subject's address in a pre-paid FedEx package to send it back and contact the subject once the device has arrived at their home (by using the mail tracking number) to schedule the first RS-tDCS session.

*device set up for the condition (active or sham), and locked (unlock codes for one-time use will be provided before each session); **day 1 being the first RS-tDCS session and no sessions on weekends. CPEP: Comprehensive Psychiatric Emergency Program; DLPFC: dorsolateral prefrontal cortex; RS-tDCS: remotely supervised transcranial direct current stimulation.

RS-tDCS sessions:

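### Section 13 takes subjects out of the study, not only off stimulation, for apparent harm, ECT/TMS or pregnancy, and does not say that their remaining safety assessments continue

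*Combined protocol and SAP*

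**What the plan says.** Section 13 (Subject Withdrawals) gives three grounds for removal that can arise after randomization:

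- Apparent harm, at the team's discretion: "Subjects may be removed from the study without their consent if they appear to be harmed by participating".
- ECT or TMS, mandatory: subjects leave "if they initiate treatment with electroconvulsive therapy or transcranial magnetic stimulation at any moment during the trial".
- Pregnancy, mandatory but limited to the period of the RS-tDCS sessions: "women subjects will be removed from the study if they become pregnant or planning to become pregnant".

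A fourth ground, failing the tolerability test, is settled at baseline. Section 8 places allocation later ("After baseline assessment, research staff not involved in the RS-tDCS supervisions and clinical assessments will randomize the subject"), so that ground does not affect follow-up of randomized subjects.

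On data after removal, Section 13 has two sentences: "No new information identifying the subject will be gathered after the withdrawal date" and "Information that has already been gathered may still be used for research purposes".

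The follow-up at issue is described elsewhere. Section 8 and Table 1 schedule remote clinical assessments, including the C-SSRS, at day 14 (+7), day 30 (+7) and day 60 (+10) from the first session. Section 4, secondary outcome 8, adds the treatment emergent event review: "after each RS-tDCS session and clinical assessment, subjects will be asked" about new symptoms, conditions and treatments. The same item says that treatment changes will be allowed for in the analysis and interpretation. Section 9 attaches the imminent-risk question to these visits.

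Section 16 requires outcome, course and causality for every adverse event. It classes suicide attempts and psychiatric hospitalizations as serious, calls them expected in this population, and puts all subjects into a Fisher comparison of the arms.

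**The concern.** Leaving treatment and leaving the study are different events, and Section 13 provides only for the second. If removal ends the assessments, three things follow.

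- An event still open at removal lacks the outcome and course that Section 16 asks for.
- Later attempts or admissions are no longer actively sought.
- Because Section 16 keeps every subject in the comparison, a removed subject counts as free of later event types that nobody asked about. The event that led to removal is kept.

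Subjects who appear harmed, or who need ECT or TMS, are among those whose later course most needs describing. They would have the least complete safety data.

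**Working it through.** There is no stated figure to reproduce: the sample size of 20 is given as a choice, and no removal rate is stated. The check sets the texts side by side and then sizes the possible loss.

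**1. Two readings of Section 13.** On the ordinary reading, a subject removed from the study has no further study visits, and only data already gathered are used. On the narrower reading, the bar covers identifying information only, so coded C-SSRS and event-review data could still be collected. No section I could read says which is meant, and none says that removed subjects keep their assessments.

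**2. The grounds differ.**

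- *ECT/TMS* applies for the whole trial. Ten sessions on consecutive weekdays end between day 12 (Monday start) and day 14 (other starts); the feasibility criterion allows three weeks from receipt of the device. Removal for ECT on, say, day 35 would then stop no stimulation. It would lose the day 60 assessment, and the day 30 assessment too if that was still pending in its window to day 37. The plan to allow for treatment changes (Section 4, item 8) already addresses confounding.
- *Pregnancy* applies only while sessions run, so stopping stimulation has a purpose. Ending the remote assessments is a separate step.
- *Apparent harm* is discretionary. Section 9 can hold the next session after an event of critical concern without removal, but Section 13 does not refer to that step. The hold does not cover ECT/TMS or pregnancy.

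**3. Follow-up lost per removed subject, ordinary reading.** Days lost = end of follow-up minus removal day. The end is day 60, or day 60 + 10 = 70 if the last visit falls at the end of its window.

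| Removal | Days lost, end at day 60 | Days lost, end at day 70 | Assessments lost |
|---|---|---|---|
| Day 2 | 58 | 68 | 3 |
| Day 12 | 48 | 58 | 3 |
| Just after the day 14 visit, held on day 14 | 46 | 56 | 2 |
| Just after the day 14 visit, held on day 21 | 39 | 49 | 2 |
| Just after the day 30 visit, held on day 30 | 30 | 40 | 1 |
| Just after the day 30 visit, held on day 37 | 23 | 33 | 1 |
| After the day 60 visit | 0 | 0 | 0 |

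On the narrower reading the loss may be zero in every row.

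**4. Share of the trial.** With 20 subjects randomized 1:1, there are about 10 per arm and 20 × 3 = 60 planned assessments. One removed subject is 1/20 = 5% of the trial and about 1/10 = 10% of an arm. Assume 0 to 2 removals per arm, all grounds together. That is 0 to 4 in total and, if all occur before day 14, 0 to 12 of 60 assessments (0% to 20%).

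**5. Effect on a later event type.** If x events are seen among 10 and k subjects were removed, the true proportion lies between x/10 and (x + k)/10. The uncertainty is 0 points for k = 0, up to 10 for k = 1 and up to 20 for k = 2. One missed event turns 1/10 (exact 95% upper limit 44.5%) into 0/10 (upper limit 30.8%).

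**6. Effect on the Fisher test.** For k v 0 events at 10 per arm, two-sided p = 2 × C(10,k)/C(20,k):

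- 1 v 0: 2 × 10/20 = 1.00
- 2 v 0: 2 × 45/190 = 0.47
- 4 v 0: 2 × 210/4845 = 0.087
- 5 v 0: 2 × 252/15504 = 0.033

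At low counts a missed event changes nothing. One missed event would move 5 v 0 to 4 v 0 and cross 0.05, but counts that high for later serious events are unlikely here.

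**The case against.** The strongest reply is that the text does not order follow-up to stop. Section 13 bars only new identifying information, and Sections 14 and 16 distinguish identifiers from coded research data. A reader might infer that the protocol cancels these visits; it does not say so. This part stands: the finding is an ambiguity whose ordinary reading loses data, not an established loss. It still leaves staff unable to tell whether to make the day 30 call.

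Second, Section 16 asks for outcome and course of all adverse events, with no exception for removed subjects. That could be read as requiring an open event to be followed. It does not provide for finding new events later.

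Third, ending participation can protect a subject harmed by taking part, since Section 9 recognizes that assessments themselves may cause stress. This stands, and the change needs an exception for it.

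Fourth, removal for harm is probably rare: the home-tDCS report cited in Section 9 found no serious events and no discontinuation for intolerability over 6,779 sessions. Clinical safety does not rest on study visits alone either, because subjects agree to remain in outpatient care and a safety plan is provided for. Both points stand and lower the priority. The consent form's withdrawal wording is not available here and might settle the question.

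**Conclusion.** The point holds as a cheap, low-priority improvement. Section 13 makes leaving the study the consequence of three post-randomization events, and nothing in the plan preserves the remaining safety assessments. The case is clearest for ECT or TMS started after the sessions end.

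On the ordinary reading the loss is up to three assessments and 58 to 68 days for a removal on day 2, falling to nothing after the day 60 visit; on the narrower reading it may be zero. The trial-level figures rest on an assumed 0 to 2 removals per arm.

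A reader might infer that the safety comparison will be biased or its result wrong. The documents do not support that: nothing shows that removal would differ by arm, so no direction can be claimed, and the change in Fisher significance needs unlikely counts. The primary outcome counts completed sessions, so whether assessments continue after removal does not affect it.

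**What to change.** In Section 13, separate stopping stimulation from leaving the study:

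- For apparent harm, ECT/TMS and actual or planned pregnancy, stop any remaining stimulation and keep the planned remote day 14, 30 and 60 C-SSRS and event reviews. The exceptions are a subject who withdraws consent and assessments that are themselves the source of harm; Section 9 already lets staff stop those.
- Follow the event that led to stopping until it resolves or until the day 60 visit.
- Apply the sentence on no new information only to subjects who withdraw consent.
- If no session took place, time the visits from discharge or device delivery. Randomization is not a suitable start, because Section 8 places it before discharge.
- Use hospital record checks only if the signed consent covers the period. Section 7 authorizes access to records on "admission and discharge dates, suicidal ideation, method and circumstance of self-harming behavior, diagnoses, and medication" but gives no time span.

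In Section 16, count later events in the randomized arm. Report by arm the number taken off stimulation, with reasons, and the number completing follow-up.

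The cost is an edit to these sections and to the consent wording, plus at most three remote assessments per removed subject (3 × $30 = $90, already within the planned payments of Section 12). Under the assumed 0 to 4 removals that is 0 to 12 calls and $0 to $360. The downside is a few calls to subjects no longer receiving sessions, which some may decline.

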5. INCLUSION AND EXCLUSION CRITERIA

Inclusion criteria:

- age between 18 and 65 years

- diagnosis of mood or bipolar disorder registered in the electronic hospital medical record

- history of suicidal ideation and/or suicide behavior at the time of admission registered in the electronic hospital medical record

- absent of suicidal ideation at the time of enrollment (defined as questions 1 and 2 of the C-SSRS answered "no").

- ability and willingness to provide information and permission to contact at least one person in the case of a need to contact them to promote subject safety or inability to reach the subject for follow-up

- a living situation with access to a private space suitable for administration of the RS-tDCS sessions in next three weeks

- agree to use a medically acceptable form of birth control while receiving the treatment if you are an individual able to become pregnant

- living in Monroe County region, as this is the area covered by the Mobile Crisis Team, a URMC psychiatric emergency team serving anyone within Monroe County

- device or computer with internet access for a URMC-approved remote RS-tDCS supervision

- ability to manage proper use of the device in a practice session

Exclusion criteria:

- acute psychiatric instability or substance abuse (e.g., psychotic symptoms, alcohol misuse in the previous three months, use of any illicit drugs in the previous three months)

- unstable medical condition with reduction of functional capacity

- history of epilepsy or seizures in the last year

- history of neurodegenerative diseases registered in the electronic hospital medical record
- presence of or implanted any ferromagnetic metal in the head or the neck
- pregnant or breastfeeding or willingness to become pregnant in the next month

- history of head trauma (e.g., head injury, brain injury) or neurosurgery
- history of skin disorder or sensitive skin area near stimulation locations
- the presence of pacemaker
- current treatment with electroconvulsive therapy or transcranial magnetic stimulation

Although concurrent treatment with medications or psychotherapy is not an exclusion criterion, we will measure changes in medication and psychotherapy for descriptive and planning purposes (please, see "Secondary outcome measures", item 9).

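### Starting ECT or TMS removes a subject from all follow-up, so up to three visits of secondary-outcome scores are lost for a plausibly outcome-related reason

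*Combined protocol and SAP*

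**What the plan says.** Section 13 (Subject Withdrawals) states that subjects are "removed from the study if they initiate treatment with electroconvulsive therapy or transcranial magnetic stimulation at any moment during the trial". On data, it adds that "No new information identifying the subject will be gathered after the withdrawal date" and that "Information that has already been gathered may still be used for research purposes". Its pregnancy rule, by contrast, is limited to the period of the stimulation sessions.

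Section 5 separately lists "current treatment with electroconvulsive therapy or transcranial magnetic stimulation" as an exclusion at entry.

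Section 8 (Study Procedures) has the clinical questionnaires "re-administered at day 14 [+ 7 days], day 30 [+ 7 days], and day 60 [+ 10 days] from the first RS-tDCS session", and gives a participation time of up to 70 days. Randomisation comes earlier, before discharge: "After baseline assessment, research staff not involved in the RS-tDCS supervisions and clinical assessments will randomize the subject".

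Section 4, secondary outcome 8, records new treatments because "changes in treatment will help researchers to account for them in data analysis", but names no method. Section 17 compares groups at each time point with a t-test or chi-square test. It states no efficacy analysis set and no rule for missing scores. The statement in section 16 that all subjects are included applies only to the adverse-event comparison.

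**The concern.** The ten sessions take place on weekdays and are expected within three weeks of receiving the device, but the removal rule runs to the last visit, well after stimulation has ended. A rule on concurrent ECT or TMS is not questioned here. The question is why measurement should also stop.

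All subjects have a mood or bipolar disorder and were admitted with suicidal ideation or behaviour. The secondary outcomes measure ideation, rumination, associated symptoms and depression. If ECT or TMS is started because a subject is doing badly, the rule deletes the scores that would have shown it. Secondary outcome 3 uses these visits to determine how many subjects relapsed, and Hypothesis 2 uses the end-of-treatment C-SSRS result to supply an effect size for a full trial. Recording the treatment change does not recover scores that were never collected.

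**Working it through.** **Inputs from the documents.** 20 subjects randomised 1:1, so about 10 per arm; visits at day 14 (+7), 30 (+7) and 60 (+10) from the first session; $30 per clinical assessment (section 12); cited dropout of 22% to 25% (section 17). The plan gives no power, SD, expected effect or ECT/TMS start rate, so it has no figure of its own to reproduce.

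**Visits lost, by time of start.**
- Before the day 14 visit (day 14-21): up to 3. Only this case reaches the end-of-treatment comparison in Hypothesis 2.
- Between the day 14 and day 30 visits (the latter at day 30-37): 2.
- Between the day 30 and day 60 visits (the latter at day 60-70): 1.

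**Illustration (assumed values).** At one visit, 5/10 sham and 3/10 active subjects have ideation; those with ideation score 15 on C-SSRS intensity and the others 0. Difference = sham proportion minus active proportion. d = 15 × difference / pooled SD, where pooled variance = [n₁ × 225 × p₁(1−p₁) + n₂ × 225 × p₂(1−p₂)] / (n₁ + n₂ − 2). With nobody lost: 5/10 − 3/10 = 20.0 points; pooled SD = √[(562.5 + 472.5)/18] = 7.58; d = 3.0/7.58 = 0.396.

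| Subject concerned | Calculation | Points | d |
|---|---|---|---|
| None lost | 5/10 − 3/10 | 20.0 | 0.396 |
| Sham with ideation, lost | 4/9 − 3/10 | 14.4 | 0.286 |
| Active without ideation, lost | 5/10 − 3/9 | 16.7 | 0.324 |
| Sham without ideation, lost | 5/9 − 3/10 | 25.6 | 0.507 |
| Active with ideation, lost | 5/10 − 2/9 | 27.8 | 0.569 |
| Sham, resolved on ECT/TMS, score kept | 4/10 − 3/10 | 10.0 | 0.200 |
| Active, resolved on ECT/TMS, score kept | 5/10 − 2/10 | 30.0 | 0.629 |

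The d column bears on Hypothesis 2 only for starts before the day 14 visit. Over all combinations of two losses, the extremes are 3/8 − 3/10 = 7.5 points (two sham with ideation) and 5/10 − 1/8 = 37.5 points (two active with ideation).

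**Sampling error.** For d = 0.396 with 10 per arm, t = 0.396 × √5 = 0.885 on 18 degrees of freedom. Inverting the noncentral t gives a 95% interval for d of −0.50 to 1.28.

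**What the shift would mean for planning.** Assuming a two-sided 5% level and 80% power, a later trial needs about 102 per arm at d = 0.396, 193 at 0.286 and 50 at 0.569.

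**Comparison with ordinary dropout.** If the cited rates applied here, 0.22 × 20 = 4.4 and 0.25 × 20 = 5 subjects, more than the 0 to 2 ECT/TMS starts assumed above.

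**The case against.** **Materiality.** No start rate is given, the number may be zero, and all the sizes above are illustrations. Sampling error exceeds every shift, only early starts reach Hypothesis 2, and section 17 has a wider missing-data gap that ordinary dropout would expose more often. All of this stands, and it limits the weight of the point. It does not remove it, because here a stated rule discards scores that could be collected.

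**Bias.** A reader might infer that the rule biases the effect estimate, and that keeping the later scores corrects it. The documents do not support that, because they state no estimand. In the illustration, a resolved score that is kept moves d to 0.20 or 0.63, further from 0.40 than losing the same subject does (0.29 or 0.57). The two analyses answer different questions.

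**Direction.** A reader might also infer that the rule hides a benefit by removing the worst sham subjects. In a simulation with an assumed true d of 0.8, removing the worst one, two or three sham subjects shrinks the mean difference to 0.63, 0.48 or 0.35 SD. That is a one-sided extreme; nothing in the documents says which arm would lose subjects.

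**Hidden relapse.** Keeping scores can itself mislead: a subject who relapses between visits and improves on ECT or TMS may look free of ideation at the next visit. This stands, and the fix must deal with it.

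**Existing records.** The C-SSRS screening version after each session, the treatment-emergent event review and the SAE reports may already hold ideation or events from before an early start. This partly mitigates the loss. The screening version, however, serves risk assessment and is not a listed outcome.

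**Wording.** The bar on new information covers only information identifying the subject, so it is weak evidence that coded scores are barred. The stronger evidence is removal from the study, with no provision for later visits.

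**Conclusion.** The point holds as one of avoidable, potentially informative missing data in secondary estimates. As written, the rule ends follow-up for any subject who starts ECT or TMS up to the day 60 (+10) visit, and costs one to three visits of scores.

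The link to outcome is an inference from the population and the outcomes measured. The number affected is unknown (0 to 2 of 20 is an assumption; zero means no effect), and the direction is not fixed. If one subject were affected, the illustrated difference of 20.0 points could move to between 14.4 and 27.8, well inside sampling error. It should be corrected because it is cheap to avoid, not because it would decide the trial.

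A reader might infer that the feasibility result is compromised. It is not: that outcome counts completed sessions, and does not rest on the later scores discussed here.

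**What to change.** - Reword section 13 so that starting ECT or TMS does not by itself end follow-up. Whether and when stimulation stops is for the sponsor to state.
- Continue the scheduled remote day 14, 30 and 60 assessments unless the subject withdraws consent.
- In section 17, compare groups as randomised using all collected scores. Add one sensitivity analysis that excludes scores after ECT or TMS starts, and say that the two answer different questions.
- Report ECT/TMS starts by arm and timing, with any ideation recorded before the start (session screening version or earlier visits), so that a relapse followed by improvement is not hidden.
- Visits are dated from the first session but randomisation precedes discharge. Report by arm any subject who starts ECT or TMS before session 1 and so has no visit dates.

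**Cost.** Protocol and analysis wording, plus consent wording if it repeats the rule. Section 12 already provides $30 "for each clinical assessment (day 14, day 30, and day 60 from the first RS-tDCS session"), so each affected subject needs 1 to 3 planned assessments: 1 × $30 to 3 × $30 = $30 to $90 in payments, plus staff time already scheduled. Two subjects would cost at most 2 × 3 × $30 = $180 in payments. The downside is that later scores also reflect ECT or TMS, which is why the sensitivity analysis and the report of starts are needed.
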